3.7.2.2 Change in Lee Symptom Scale Score (LSS)

The Lee cGVHD Symptom Scale consists 30 items of 7 domains: skin, eyes and mouth, breathing, eating and digestion, muscles and joints, energy, and mental and emotional. Each question is scored 0, 1, 2, 3 or 4.

Kadmon Corporation

Page 16 of 26

A domain score will be calculated for each domain by taking the mean of all items completed if more than 50% were answered and normalizing to a 0 to 100 scale. A summary score will be calculated as average of all non-missing domain scores if more than 50% of them are non-missing. A higher score indicated more bothersome symptoms. 7 points difference on the summary score of cGVHD symptom scale was found to be clinically meaningful. In the above formulas, m is the number of items have non-missing value in a domain, and n is the number of domains have non-missing domain scores.

Raw
$$Score = \frac{I_1 + \dots + I_m}{m}$$
, $Domain Score = (Raw Score/4)*100$

$$Summary Score = \frac{Domain Score_1 + \dots + Domain Score_n}{n}$$

In the above formulas, m is the number of items have non-missing value in a domain, and n is the number of domains have non-missing domain scores.

Analyses will include:

- Both score and change-from-baseline values (summary score and domain scores) will be summarized as continuous variables by visit
- Number and percent of subjects with a ≥7-point reduction from baseline (C1D1)
- Number and percent of subjects with a ≥7- point reduction from baseline on at least 2 consecutive post-baseline assessments.
- Duration of a 7-PtR (DO7-PtR) (defined as time from documentation of the first ≥7-point reduction to the first documentation of less than 7-point reduction). If there are multiple episodes, then DO7-PtR will be measured as the sum of DO7-PtR from all episodes.

These analyses will be performed on Full Analysis Set.

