## Disposition of Subjects

Overall, 64 subjects were screened for the study of whom 54 were included in the modified Intent-to-Treat (mITT) Population: 17 subjects in Cohort 1, 16 subjects in Cohort 2, and 21 subjects in Cohort 3. As of the cut-off date for this analysis (19 February 2020), 47 (87.0%) subjects have discontinued treatment and 7 (13.0%) subjects remain on treatment with

belumosudil. The most frequent reason for treatment discontinuation was disease progression (22 [40.7%] subjects). A total of 37 (68.5%) subjects were participating in the study, either being actively treated with belumosudil or being followed for survival (in Long-term Follow-Up). Seventeen (31.5%) subjects have discontinued from the study for the following reasons: 11 (20.4%) subjects died, 5 (9.3%) subjects were lost to follow-up, and 1 (1.9%) subject discontinued for other reasons. The overall median follow-up duration was 28.8 months: 35.9 months for Cohort 1; 32.4 months for Cohort 2; and 24.0 months for Cohort 3.

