# Disposition of Subjects

Overall, 132 subjects received at least 1 dose of belumosudil: 66 subjects in Arm A and 66 subjects in Arm B.

As of the cutoff date, 19 February 2020, the median follow-up duration was 7.9 months: 8.0 months for Arm A and 7.9 months for Arm B. In total, 62 (47.0%) subjects had discontinued from treatment; 70 (53.0%) remain on treatment with belumosudil. The most frequent reasons for treatment discontinuation were progression of cGVHD (16 [12.1%] subjects) and withdrawal by subject (14 [10.6%]). A total of 119 (90.2%) subjects participated in the study, either actively treated with belumosudil or followed for survival. Thirteen (9.8%) subjects had discontinued from the study: 8 (6.1%) subjects died; 3 (2.3%) subjects withdrew; 1 (0.8%) subject lost to follow-up; and 1 (0.8%) subject for which data was missing.

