2.2 Study Design

KD025-217 is a Phase 2, open-label, extended treatment and follow-up study in subjects with cGVHD who have been previously treated with belumosudil in Study KD025-208 or in Study KD025-213.

Subjects who have signed the Informed Consent Form (ICF) will be enrolled in Study KD025-217 if they have met any of the following conditions:

- Actively receiving belumosudil in Study KD025-208 or in Study KD025-213 (excluding adults in the Companion Study and excluding adolescents enrolled under KD025-213 Amendment 2 [01June 2020])
- Is in long-term follow-up (LFTU) on Study KD025-208 or Study KD025-213. Long-term follow-up will be defined as the period after ending treatment with belumosudil and until an FFS event occurs.
- Adult enrolled in the Companion Study as specified in Study KD025-213 Amendment 2 (01 June 2020) and received at least 6 months of treatment or is in LTFU.

After signing the ICF, at Baseline, subjects will undergo efficacy assessments by Clinician-reported Global cGVHD Activity Assessment, response assessment, pulmonary function tests (PFTs), LSS score, and documentation of corticosteroid dosage and/or other therapies for cGVHD.

Subjects will undergo safety assessments including symptom-directed Physical Exams (PE), vital signs, weight, height, Karnofsky Performance Scale (KPS), hematology and clinical chemistry laboratory testing, pregnancy testing, 12-lead Electrocardiogram (ECG), documenting concomitant medications, and monitoring for Adverse Events (AEs). Subjects will continue on their same dosing regimen they received in Study KD025-208 or Study KD025-213: belumosudil 200 mg QD, 200 mg BID, or 400 mg QD. If the Investigator reduced the subject's dose of belumosudil in either Study KD025-208 or Study KD025-213, the subject will continue to receive that same reduced dose treatment with belumosudil throughout Study KD025-217 or until the AE that led to the temporary dose reduction has resolved, in which case the dose treatment can resume at the original dose at the discretion of the Investigator. Subjects will begiven a study drug diary to record daily dosing. Subjects may be administered the first dose either in the clinic or self-administered at home.

At 3 months after Baseline and every 3 months thereafter (± 14 days), subjects will report to the clinic for the same efficacy and safety assessments and dispensing of belumosudil at Baseline.

Kadmon Corporation

Page 8 of 26

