3.1.5 Baseline

Baseline value for efficacy analyses is defined as the valid and last non-missing value obtained within 28 days prior to subject receiving the first study medication in parent study KD025-208/KD025-213.

Baseline value for safety analyses is defined as the "Baseline" visit from KD025-217.

Baseline can be the day before the first study medication or on the same day as the first study medication if a pre-dose assessment is available. Subjects without data on a parameter before the first study medication will have a missing baseline for this parameter.

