3.7.2.8 Change in corticosteroid dose

Corticosteroid doses will be presented as mg/kg/day prednisone equivalent dose. Any corticosteroid dose increases to ≥ 0.9 mg/kg PE during the study is counted as new systemic cGVHD therapy.

Descriptive statistics for the Full Analysis Set will be provided for:

- Both prednisone equivalent dose and change-from-baseline values (summary score and domain scores) will be summarized as continuous variables by visit
- Change and % change from baseline to the greatest corticosteroid dose reduction at any post-baseline visit
- Number and % of subjects who reduced systemic corticosteroid dose at any postbaseline visit
- Number and % of subjects who ever discontinued systemic corticosteroid usage at any post-baseline visit

If subjects are not using prednisone as the systemic corticosteroid, then the prednisone dose equivalent will be determined according to following conversion ratios2:

1 mg prednisone is equivalent to:

- 4mg Hydrocortisone
- 0.8mg Methylprednisolone
- 0.15mg Dexamethasone
- 1mg Prednisolone

Kadmon Corporation

Page 19 of 26

0.8mg Triamcinolone

3.7.2.9 Change in cGVHD Global Severity Rating based on the Clinician-reported Global cGVHD Activity Assessment

The Clinician-reported global cGVHD Activity Assessment is a 0-10 point numeric rating scale with a score of 0 indicating "cGVHD symptoms not at all severe" and a score of 10 being "Most severe cGVHD symptoms possible". The activities are assessed on at baseline and then every 3 months after.

Change from baseline in cGVHD severity based on the Clinician-reported global cGVHD Activity Assessment will be summarized as a categorical endpoint at all scheduled assessment visits.

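### By-visit tables of LSS, steroid dose and global severity take change from the parent-study baseline but, as written, count visits from rollover, so extension rows pool different times since first dose

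*SAP*

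**What the plan says.** - **Origin of change.** SAP 3.1.5 takes the efficacy baseline as the last valid value obtained "within 28 days prior to subject receiving the first study medication in parent study KD025-208/KD025-213". SAP 3.7.2.2 names C1D1 for the LSS responder count.
- **How results are tabulated.** For LSS (SAP 3.7.2.2): "Both score and change-from-baseline values (summary score and domain scores) will be summarized as continuous variables by visit". SAP 3.7.2.8 says the same of prednisone-equivalent dose. Under SAP 3.7.2.9, change in global severity "will be summarized as a categorical endpoint at all scheduled assessment visits".
- **Visit clock.** SAP 2.2 places clinic visits "At 3 months after Baseline and every 3 months thereafter", where Baseline is the KD025-217 visit. SAP 2.3 adopts the schedule in Appendix A of the KD025-217 protocol.
- **Study day.** SAP 3.1.4 counts post-dose study days from the start of treatment in the parent study. No section turns that study day into visits or analysis windows.
- **Who enters.** Protocol 4.3 admits subjects from KD025-208, from main KD025-213 and from the later Companion Study. Protocol 6.2.2 gives subjects who enter already in long-term follow-up (LTFU) only LTFU contacts.

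**The concern.** The change starts on one clock and is tabulated on another. Two subjects in the same Month 3 row share a time since rollover, but their change scores cover different lengths of time since first dose. The KD025-217 Baseline visit itself becomes a row of post-treatment change at no fixed duration.

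This sits badly with the rest of the plan. OS and TTNT run from first belumosudil dose or first treatment, and the interim analysis (Protocol 9.6) is tied to 3 years of treatment. A by-visit table on the rollover clock has no row for 3 years of treatment.

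The study asks about long-term efficacy, so a reader will use these tables to judge whether benefit persists. Dose group matters too. The 400 mg QD regimen was used only in KD025-208, while both 200 mg groups draw on both parent studies. Any display by dose group at a given extension visit therefore mixes dose with time since first dose.

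**Working it through.** The plan gives no figure for the spread in time since first dose, so there is nothing to reproduce directly. As a check on the inputs, the on-treatment percentages do reproduce: 7/54 = 13.0% (KD025-208) and 70/132 = 53.0% (KD025-213).

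**Inputs**
- KD025-208 median follow-up at 19 Feb 2020 (Protocol 1.4.1): 28.8 months overall; "35.9 months for Cohort 1; 32.4 months for Cohort 2; and 24.0 months for Cohort 3".
- KD025-213 at the same cut-off (Protocol 1.4.2): "the median follow-up duration was 7.9 months: 8.0 months for Arm A and 7.9 months for Arm B".
- Last KD025-213 subject's first visit: 6 months before that cut-off (Protocol 1.4.2, Efficacy).
- Companion Study amendment date: 01 June 2020. Active Companion subjects need at least 6 months of treatment (Protocol 4.3).
- Rollover date: not given. For illustration only, the date of protocol Amendment 1, 08 Sep 2021 (SAP 1).

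**Step 1: gap between parent studies.** Time since first dose at rollover ≈ F + D, where F is median follow-up at the cut-off and D is months from cut-off to rollover. With a common rollover date D cancels, leaving F₁ − F₂.

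| Comparison | Gap (months) |
|---|---|
| KD025-208 overall vs KD025-213 | 28.8 − 7.9 = 20.9 |
| Cohort 1 vs KD025-213 | 35.9 − 7.9 = 28.0 |
| Cohort 2 vs KD025-213 | 32.4 − 7.9 = 24.5 |
| Cohort 3 vs KD025-213 | 24.0 − 7.9 = 16.1 |

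Within one dose group the gap is similar: 200 mg QD, 35.9 − 8.0 = 27.9; 200 mg BID, 32.4 − 7.9 = 24.5.

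**Step 2: sensitivity to the common-date assumption.** If KD025-208 subjects rolled over d months earlier than KD025-213 subjects, the gap falls by d; if later, it rises by d. For the overall 20.9 months, 6 months either way gives 14.9 to 26.9, and 12 months gives 8.9 to 32.9.

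**Step 3: illustration at 08 Sep 2021.** From 19 Feb 2020 this is 567 days / 30.4375 = 18.6 months. The Month 3 visit then falls at F + 18.6 + 3:
- Cohorts 1, 2 and 3: 57.5, 54.0 and 45.6 months.
- Main KD025-213: 7.9 + 18.6 + 3 = 29.5 months.
- Active Companion subjects: from 6 + 3 = 9 months up to 15.2 + 3 = 18.2 months, since 01 June 2020 to 08 Sep 2021 is 464 / 30.4375 = 15.2 months.

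**Step 4: Companion against main KD025-213.** At a common date the last main subject is at 6 + 18.6 = 24.6 months and a Companion subject at most at 15.2, a gap of at least 24.6 − 15.2 = 9.4 months. This takes first visit as first dose; if first visit was the start of the 2-week screening, the gap is about 8.9.

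**Step 5: who fills the rows.** LTFU entrants have no clinic visits. At the cut-off 7 + 70 = 77 subjects were on treatment, of whom 7/77 = 9.1% were from KD025-208. Any 400 mg QD subject still on treatment is necessarily among those 7.

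**The case against.** The best defence is that the SAP does not define visit and may intend more than the extension schedule. Study day runs from the parent first dose, response is judged against parent C1D1, and exposure and DOR are reported out to 36 months. Parent-study visits could be meant to appear in these tables. That is possible, but it is not written, and extension rows would stay misaligned unless they were re-windowed.

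Four further points stand:
- A reader might infer that the by-visit tables are the only planned view of these endpoints. They are not. LSS also has the duration of a 7-point reduction and a count of reductions held on two consecutive assessments. Steroid dose has greatest reduction, any reduction and ever discontinued. None of these depends on visit labels.
- A reader might infer that one row is known to mix 2.5-year and nearly 5-year changes. The documents do not establish this. It rests on an assumed entry date and on medians that include subjects who had stopped treatment or died. The widest gap comes from a small minority of active subjects.
- A reader might infer that the rows are meaningless or that a dose comparison is invalid. Each row is a defined time since rollover, and change from pre-treatment among those still treated is a fair descriptive question. The protocol has no formal hypothesis, so no test is affected.
- For steroids, Protocol 6.3 speaks of change during the study, so the baseline is less certain there than SAP 3.1.5 suggests.

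**Conclusion.** The point holds as a mismatch in descriptive tables. Measured from the parent baseline and indexed by the only schedule the SAP supplies, the extension rows for LSS, steroid dose and global severity pool different times since first dose.

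The likely spread between KD025-208 and main KD025-213 is about 21 months (16 to 28 by cohort), with active Companion subjects at least about 9 months behind the last main KD025-213 subject. These figures assume a common rollover date and use whole-cohort median follow-up as a stand-in for time since first dose in those who rolled over. The documents do not give the true values, and the composition at rollover may differ from the 7 and 70 on treatment in February 2020.

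What is affected is the reading of trends over time and of differences between dose groups, most of all for 400 mg QD. The visit-independent summaries are not misaligned. The documents do not support discarding the nominal-visit tables.

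**What to change.** In SAP 3.7.2.2, 3.7.2.8 and 3.7.2.9:

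1. Add summaries in analysis windows on the SAP 3.1.4 study day, that is, time since first belumosudil dose in the parent study. For example, use 6-month windows and take the assessment closest to the target day. Combine parent and KD025-217 assessments, and show n by parent study in each window.
2. Keep the nominal KD025-217 visit tables, label them as time since rollover, and pair them with change from KD025-217 Baseline.
3. State the steroid baseline explicitly, so that SAP 3.1.5 and Protocol 6.3 agree.

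The cost is SAP wording, a window derivation and some extra tables. No new data collection is needed: the efficacy baseline already requires parent-study records, and LSS, steroid dose and global severity are all recorded at KD025-217 Baseline. The downside is that late windows will be small and made up mainly of KD025-208 subjects, so a trend across windows can reflect changing composition. Showing n by parent study makes that visible.

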3.7.2.3 Time to Next Treatment (TTNT)

The TTNT will be measured as the time from first treatment to the time of new systemic cGVHD treatment (which will be defined by clinical team review), censored by last response assessment or long term follow up assessment, whichever is the latest and available. TTNT will be analyzed

Kadmon Corporation

Page 17 of 26

by the Kaplan-Meier survival method as well as the landmark analysis at 6, 12, 18, and 24 months.

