#### 4.6 Withdrawal Criteria

Subjects will receive belumosudil treatment until clinically significant progression of cGVHD (defined as progression requiring addition of new systemic therapy for cGVHD), histologic recurrence of underlying malignancy, unacceptable toxicity, Investigator decision, subject preference/withdrawal of consent, loss to follow-up, Sponsor decision, or death (whichever occurs first).

Subjects who experience cGVHD progression as defined by NIH criteria but for whom no new systemic therapy is planned may continue to receive belumosudil and be assessed again at their next visit. If progression per NIH criteria is not confirmed or no new systemic therapy is planned, subjects may continue on belumosudil at the Investigator's discretion until subjects fulfill at least 1 criterion requiring discontinuation of study drug.

Belumosudil may be tapered after a sustained response for 6 months and cessation of all other immunosuppressants for at least 3 months. The tapering schedule for belumosudil is described in Dosage and Administration 5.2.

Subjects may be withdrawn from study treatment at any time by the Investigator or the Sponsor if it is considered detrimental for the subject to continue in the study. The reason for withdrawal will be captured in the eCRF.

Subjects have the right to withdraw from the study at any time and for any reason without prejudice to their future medical care by the physician or at the institution. If the subject wishes to voluntarily withdraw from the study, the physician will consult with the subject regarding procedures for safe withdrawal. Every effort should be made to have such subjects attend protocol visits including the 28-day Follow-up Visit. Reasons for withdrawal of consent will be captured in the eCRF. Subject data up to withdrawal of consent will be included in the analysis of the study, and where permitted, publicly available data can be included after withdrawal of consent.

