### 6.2.5 Long-term Follow-up

Long-term Follow-up will start at Baseline for enrolled subjects who have been permanently discontinued from belumosudil in Study KD025-208 or in Study KD025-213 where they have not yet had an FFS event. The LTFU will occur after the 28-day Follow-up Visit has been completed for enrolled subjects who were actively dosed with belumosudil at Baseline.

Subjects will have LTFU approximately every 3 months until an FFS event occurs. This LTFU assessment will occur by subjects being contacted by telephone, e-mail, or postal mail to confirm survival status, any initiation of new systemic cGVHD therapies, and relapse of underlying disease. Alternatively, this information may be obtained from the subject's medical records.

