3.2 Analysis Populations

Full Analysis Set: The Full Analysis Set is defined as all subjects enrolled in the study. All safety and efficacy analyses will be performed on the Full Analysis Set.

There are 3 treatment groups for this study: belumosudil 200 mg QD, 200 mg BID, and 400 mg QD. Each subject's treatment group is determined by their originally assigned dosing cohort (Study KD025-208) or randomized arm (Study KD025-213).

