3.7.2.4 Failure-free-survival (FFS)

FFS is defined as the absence of new cGVHD systemic therapy, non-relapse mortality and recurrent malignancy (i.e., underlying disease) and is censored by last response assessment or long term follow up assessment, whichever is the latest and available. Kaplan-Meier plots, descriptive statistics of FFS and landmark FFS at 6, 12, 18, 24, 30 and 36 months will be provided. In addition, analyses for the three components of FFS will also be provided.

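### TTNT by Kaplan-Meier censors death, so 1 − KM is at or above the cumulative incidence of new therapy in the same subjects; the FFS components have no named estimator

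*SAP*

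**What the plan says.** SAP 3.7.2.3 measures TTNT as "the time from first treatment to the time of new systemic cGVHD treatment", "censored by last response assessment or long term follow up assessment, whichever is the latest and available. TTNT will be analyzed" "by the Kaplan-Meier survival method as well as the landmark analysis at 6, 12, 18, and 24" months. Death and relapse are neither events nor mentioned as reasons for censoring.

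SAP 3.7.2.4 defines FFS as a composite of new systemic cGVHD therapy, non-relapse mortality and recurrent malignancy, with landmarks from 6 to 36 months. It then adds: "In addition, analyses for the three components of FFS will also be provided". No estimator is given for those analyses.

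Two protocol sections determine when follow-up for new therapy stops. Section 4.6 ends belumosudil on, among other reasons, "histologic recurrence of underlying malignancy, unacceptable toxicity, Investigator decision". Section 6.2.5 says: "Subjects will have LTFU approximately every 3 months until an FFS event occurs".

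On the analysis set, SAP 3.2 says: "The Full Analysis Set is defined as all subjects enrolled in the study". The TTNT clock nevertheless starts at first belumosudil dose (Protocol 6.3), which was taken in the parent study.

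**The concern.** A subject who dies without new therapy can no longer start one. Kaplan-Meier with that death censored treats the subject as keeping the same future chance of new therapy as those still under observation. The quantity 1 − KM then describes a setting in which nobody dies. It is not the share of subjects who actually go on to another systemic treatment, which is how a TTNT landmark is likely to be read.

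Relapse differs. It does not preclude new cGVHD therapy, but under the protocol it ends treatment and then follow-up contact, so new therapy after relapse will largely go unrecorded.

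The same issue reaches the FFS decomposition. New therapy, non-relapse mortality and recurrent malignancy are mutually exclusive first failures that together make up 1 − FFS. Cumulative incidence curves add to that total; separate 1 − KM curves do not. If Kaplan-Meier were used for the components, the report would contain a TTNT figure and a decomposition that disagree with its own FFS curve.

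**Working it through.** The documents give no TTNT probability, event count or power calculation, so there is no planned figure to reproduce. The size has to be illustrated with assumed rates.

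**Inputs from the documents**
- Deaths in KD025-208: 11/54 = 20.4%, median follow-up 28.8 months (Protocol 1.4.1). Crude rate 11 / (54 × 28.8/12) = 0.085/year.
- Deaths in KD025-213: 8/132 = 6.1%, median follow-up 7.9 months (Protocol 1.4.2). Crude rate 8 / (132 × 7.9/12) = 0.092/year.
- These rates cover all treated subjects, include any deaths after new therapy, and exclude relapse, which the documents do not quantify. Enrolled survivors may have lower rates.

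**Assumptions**
- Constant rates: h1 for new therapy, 0.20–0.40/year; h2 for death or relapse, 0.06–0.15/year. If only death is treated as competing, h2 is the death rate alone.
- Entry to KD025-217 at E months after first dose. The main KD025-213 cohort had its last first visit 6 months before the 19 February 2020 cutoff, so about August 2019. The SAP cites protocol Amendment 1 of 08 September 2021. The first enrolment date is not given; E = 22 is an assumption.

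**Formulas**
- 1 − KM = 1 − exp(−h1·t)
- Cumulative incidence (CIF) = h1/(h1+h2) × [1 − exp(−(h1+h2)·t)]
- With entry at E and no event before it, replace t by t − E.

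Differences below come from unrounded values.

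**No delayed entry, 24 months (t = 2)**

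| h1 | h2 | 1 − KM | CIF | Excess (points) |
|---|---|---|---|---|
| 0.20 | 0.06 | 33.0% | 31.2% | 1.8 |
| 0.25 | 0.09 | 39.3% | 36.3% | 3.1 |
| 0.40 | 0.15 | 55.1% | 48.5% | 6.5 |

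Over the same ranges the excess is 0.1–0.6 points at 6 months and 0.5–2.2 at 12. At 36 months it is 3.5–11.1 points, but that is an FFS landmark; the TTNT landmarks stop at 24.

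**Entry at 22 months (h1 = 0.25, h2 = 0.09)**

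| Month | t − E (years) | 1 − KM | CIF, same subjects | Excess (points) |
|---|---|---|---|---|
| 24 | 2/12 | 4.1% | 4.1% | about 0 |
| 36 | 14/12 | 25.3% | 24.1% | 1.2 |
| 48 | 26/12 | 41.8% | 38.3% | 3.5 |

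**Delayed entry as its own bias.** At the same rates, the 24-month 1 − KM in enrolled subjects is 31.3%, 22.1% or 4.1% for entry at 6, 12 or 22 months, against a CIF of 36.3% in all treated subjects. Each falls below the all-treated figure.

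**Additivity, if Kaplan-Meier were used for the components.** Assume 0.25, 0.05 and 0.04/year for new therapy, non-relapse death and relapse.
- 24 months: 1 − KM values 39.3 + 9.5 + 7.7 = 56.6% (from unrounded values), against 1 − FFS = 1 − exp(−0.34 × 2) = 49.3%. The CIFs (36.3%, 7.3%, 5.8%) add to 49.3%.
- 36 months: 78.0% against 63.9%.
- 36 months with entry at 22: 35.5% against 32.7%.

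**The case against.** The strongest objection concerns direction. A reader might infer that the plan's TTNT figures will overstate the probability of needing new therapy, full stop. The documents do not support that. Only enrolled subjects are analysed, and those entering from long-term follow-up must not have had an FFS event, yet time is counted from first dose and no delayed-entry adjustment is stated. That pushes the estimate down, and at 24 months by more than the competing-risk excess in the scenarios shown. This stands, so the claim is limited to a comparison within the same subjects. It does not dispose of the point: the two biases have different causes and cannot be relied on to cancel. Nor is pre-entry time wholly free of events, since SAP 3.7.2.8 counts a corticosteroid increase to at least 0.9 mg/kg as new systemic therapy, and that could precede entry in a subject still on drug.

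A reader might also infer that the component curves will add to more than 1 − FFS. SAP 3.7.2.4 names no method, and the analyses could be counts or cumulative incidence. What stands is that the method is unspecified.

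Three further objections carry weight:
- Relapse does not rule out new cGVHD therapy, so making it a competing event changes the estimand. The fix has to say so.
- The SAP does not say that 1 − KM will be reported as a probability of needing therapy. The TTNT landmark analysis may even be a simple proportion, as the DOR landmarks in SAP 3.7.2.1 are.
- Precision is low. With about 70 subjects and no formal hypothesis, a 40% landmark has a 95% half-width of 1.96 × √(0.4 × 0.6/70) = 11.5 points, wider by dose group. The excess is mostly well inside that. It is still systematic, and composite FFS, while already planned, does not supply the new-therapy share.

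**Conclusion.** The point holds in a limited form. Kaplan-Meier is the only named TTNT estimator; censoring of death follows from the event definition, and censoring at relapse from when follow-up stops. Neither is stated in the SAP. Within the same subjects, 1 − KM is at or above the cumulative incidence of new therapy.

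The size rests wholly on assumed constant rates and entry times. It is a few points at 24 months for subjects followed from first dose, and negligible there for late entrants, in whom it emerges only at later times. The net direction against all treated subjects is not established and may well be downward. For the FFS components the finding is a missing method, with non-additivity a possible consequence and not a demonstrated one. This is a modest defect, worth correcting because the better method is standard and needs no new data.

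**What to change.** In SAP 3.7.2.3:
- Make the main TTNT estimate the Aalen-Johansen cumulative incidence of new systemic cGVHD therapy, with death before new therapy as a competing event.
- State how relapse is handled. If it is treated as competing, say that the estimand becomes new therapy before relapse, which matches the FFS component.
- Keep the Kaplan-Meier TTNT curve as a supportive figure.
- State how time between first dose and KD025-217 entry is handled.

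In SAP 3.7.2.4, name cumulative incidence for each of the three components, with the other two as competing events, so that they add to 1 − FFS. Kaplan-Meier remains right for composite FFS and for OS.

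The cost is SAP wording and a standard procedure in the stated software. The one downside is that the main TTNT figure is less directly comparable with Kaplan-Meier reports, which keeping both covers.
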